9.1 Sample Size Determination

Sample Size and Power. The purpose of this trial is not to conduct hypothesis testing, but rather to field-test the intervention to identify adherence rates to exercise prescription across a group of participants. At this time, the anticipated effect size is unknown and the sample size of 40 has been selected to maximize feasibility in the anticipated time frame for this project.

9.2 Statistical Methods

As this is the first investigation in this population to look at this resistance training, both in terms of adherence rates as well as objective and functional changes in performance, there are no published effect sizes to anticipate at this time; therefore, we have a feasibility/descriptive focus as opposed to a hypothesis-testing focus. In addition to quantitative analysis, we plan to conduct qualitative analyses from participant feedback surveys to assess barriers to participation and to improve future interventions and to increase adherence rates.

9.3 Subject Population(s) for Analysis

The populations for this investigation include:

- All-randomized population: Any subject randomized into the study, regardless of whether they received study agent
- All-treated population: Any subject randomized into the study that received at least the instructional visit of the intervention
- Protocol-compliant population: Any subject who was randomized, was allocated to the exercise group and provided at least one set of data elements required by the protocol.

9.3.1 Describe the types of analysis:

- **Primary Analysis:** The primary objective includes measuring the percentage of completed sessions compared to prescribed, and a one-sample t-test will be conducted to determine if that proportion, across participants, is >90%. A one-sample t-test will be done to determine if retention is >90%.

- **Secondary Analyses:** The secondary analyses includes measuring the objective and functional changes from pre to post intervention as well as differences between groups. Paired ANOVAs and descriptive statistics will be used to analyze functional and objective data, as well as participant feedback data, including satisfaction with each component of the intervention.
- **Exploratory, longitudinal analyses:** Content analysis will be done on the qualitative interviews to examine barriers to physical activity, as well as satisfaction with the intervention, and identification of themes to improve the intervention. Although formal hypothesis testing is not part of our specific aims, we will conduct longitudinal analyses of the data we collect to estimate potential magnitude of expected changes, as well as longitudinal analysis of the repeated measures.
- **Safety Analysis:** The safety analysis includes simple descriptive analysis about the number of adverse events over the course of the intervention between groups and across sites.

9.4 Planned Interim Analysis:

There are no planned interim analyses for this investigation.

10 Data Collection, Handling and Record Keeping

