Previous strength training interventions not optimized for rural populations. Rural areas are often underserved in terms of medical access/use and educational and economic opportunities.^{20, 21} Consequently, rural populations are diagnosed at later stages of cancer²² and have higher rates of cancer mortality.²³ Unfortunately, previous strength training research in cancer populations have mainly used supervised sessions with a personal trainer at a gym, an approach that is not feasible in many rural settings.

Overview of proposed research. To address these gaps, we propose a 2-arm pilot trial of a home-based strength training intervention (vs. waitlist control) among 40 endometrial cancer survivors. The intervention will consist of (a) an initial in-person instructional session; (b) instructional materials and resistance training equipment (e.g., resistance bands) and (c) support and feedback provided via video coaching sessions. The purpose of a pilot trial is not to conduct hypothesis testing, but rather to field-test the logistical components of the study to incorporate into a larger, future study design.²⁴ With small samples, the true effect size is more likely to be under or overestimated, therefore hypothesis testing is not valid.²⁵ Our aims are designed accordingly.

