2.2 Aims and Hypotheses

The proposed trial will determine the feasibility of an at-home resistance training protocol and measurements of exercise logging, functional fitness testing, DXA, dried blood spots and questionnaire measures. Participants will be assigned either to the resistance training program (i.e., initial in-person instructional session, telephone coaching, and self-monitoring) or to a comparison arm (wait-list control).

- **Aim 1:** To determine the feasibility of recruiting and retaining endometrial cancer survivors to a home-based resistance training 2 sessions per week of 20-40 minutes of exercise. *We hypothesize that we will meet the accrual goal and maintain >90% retention.*
- **Aim 2:** To determine participant satisfaction with each component of the intervention and identify opportunities for refinement of the intervention prior to testing in a larger study. *We hypothesize that the participants will adhere to 90% of the prescribed exercise sessions and that overall satisfaction will be high.*
- **Aim 3:** To establish that functional and objective assessments are feasible and well-tolerated in enrolled participants, as assessed using the functional fitness test (FFT) battery, dual-energy x-ray absorptiometry (DXA), finger-pricks for dried blood spots and patient-reported outcomes. *We hypothesize that these assessments will be well tolerated, as measured by the percent of participants who complete all measures and data from participant feedback questionnaires.*

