4.1.1 Primary Study Endpoints

The primary endpoint is adherence to prescribed exercise sessions as measured using exercise logging and video sessions of exercises.

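### The primary adherence test in 9.3.1 uses as its null the 90% that Aim 2 hypothesises, in a trial that says it is not for hypothesis testing

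*Combined protocol and SAP*

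**What the plan says.** Section 4.1.1 names the endpoint: "The primary endpoint is adherence to prescribed exercise sessions as measured using exercise logging and video sessions of exercises". The Primary Analysis entry in 9.3.1 measures completed against prescribed sessions and then says that "a one-sample t-test will be conducted to determine if that proportion, across participants, is >90" (per cent). The next sentence plans the same kind of test for retention above 90%.

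Aim 2 in section 2.2 sets the expectation: "We hypothesize that the participants will adhere to 90% of the prescribed exercise sessions". It has no greater-than sign, although Aim 1 in the same section uses one for retention.

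Three sections set testing aside. Section 2.1 says "The purpose of a pilot trial is not to conduct hypothesis testing, but rather to field-test the logistical components of the study" and, of small samples, "the true effect size is more likely to be under or overestimated, therefore hypothesis testing is not valid". Section 9.1 says "The purpose of this trial is not to conduct hypothesis testing, but rather to field-test the intervention to identify adherence rates". Section 9.2 describes the focus as descriptive. The exploratory paragraph of 9.3.1 itself says that formal testing is outside the specific aims. Nowhere is there an alpha, a sidedness, a power, an SD or an expected adherence above 90%, and no confidence interval for adherence is planned.

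**The concern.** A one-sided test of whether a mean exceeds 90% is designed to come out negative most of the time when the mean is 90%. If women adhere exactly as Aim 2 predicts, the primary analysis will usually say that the target was not shown. At somewhat better adherence it may still say so, depending on how much women differ.

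The plan also contradicts itself. It calls testing invalid at this size and then makes a test its primary analysis, while the quantity that 9.1 wants, the adherence rate, has no planned measure of precision. A reader planning the larger trial would receive a non-significant p-value and could take it as evidence of poor adherence.

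**Working it through.** **No figure to reproduce.** Section 9.1 chooses 40 participants for feasibility and says that the effect size is unknown. There is no power calculation.

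**Inputs from the documents**
- Exercise-arm women: 40 randomised 1:1 (8.5, Randomization), so 40 / 2 = 20. Only this arm has prescribed sessions during the trial.
- Sessions per woman: 2 per week × 10 weeks = 20 (section 8).
- Null value 90% (9.3.1); hypothesised value 90% (2.2).

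**Assumptions.** One-sided 5%; between-woman SD of adherence 10, 15 or 20 percentage points, with 5 as a favourable case.

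**Step 1: chance of success at the hypothesised value.** Under the normal model, P(reject) at a true mean of 90% equals alpha, so 5%, whatever the SD or n.

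**Step 2: the bar on the observed mean.** Bar = 90 + t(0.95, 19) × SD / √20, with t(0.95, 19) = 1.729.
- SD 5: 90 + 1.729 × 5 / 4.472 = 91.9%
- SD 10: 93.9%
- SD 15: 95.8%

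At SD 15, an observed mean of 95% would not pass.

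**Step 3: allow for bounded, skewed data.** Adherence cannot exceed 100%, so the t model is only approximate. Trials were simulated with beta-binomial adherence (20 women, 20 sessions each) and the planned test applied one-sided at 5%:

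| True mean adherence | SD 10 | SD 15 | SD 20 |
|---|---|---|---|
| 90% | 9% | 12% | 15% |
| 93% | 44% | 36% | 32% |
| 95% | 68% | 52% | 41% |

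The first row should be 5%. It is about two to three times that, so the t-test is miscalibrated for this endpoint. Left skew raises the false-success rate, even though success at 90% remains uncommon.

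**Step 4: favourable case.** With SD 5 and the t model, power at a true 95% is 99.6%. This SD is optimistic: if sessions were independent and all women alike, the SD would be √(0.95 × 0.05 / 20) = 4.9 points at 95% adherence and √(0.90 × 0.10 / 20) = 6.7 points at 90%. Any real difference between women adds to that.

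**Step 5: what estimation would give.** Approximate 95% half-width = t(0.975, 19) × SD / √20, with t(0.975, 19) = 2.093: 2.3, 4.7, 7.0 and 9.4 points for SD 5, 10, 15 and 20.

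**Step 6: the retention sentence.** Retention is yes/no for each woman. At the roughly 5% loss expected in 6.4.3, 38 of 40 are retained. The one-sided t-test against 90% then gives p = 0.080, while the exact binomial gives p = 0.22. If all 40 stay, the variance is zero and the t statistic is undefined.

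**The case against.** The strongest reply is that Aim 2's 90% means at least 90%, in line with the greater-than sign used for Aim 1 and in both tests of 9.3.1. On that reading 90% is a threshold, and any threshold test succeeds rarely at its own boundary. The reading is reasonable, but the text gives no expected value above 90%, and under the assumed SDs the chance of success at 93% is still below one half.

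A reader might infer three stronger claims that the documents do not support.
- *That a wrong decision about the larger trial follows.* No section states a go/no-go rule or ties success to a p-value. The percentage of sessions completed is to be measured in any case, and interviews and feedback also inform refinement.
- *That the test cannot confirm Aim 2, or fails about 95% of the time.* The 95% is the nominal normal-theory figure; simulated failure at a true 90% is 85-91%. At a true 95% the test succeeds in 41-68% of trials.
- *That at SD 20 the observed mean must reach 97.7%.* The formula gives that number, but it cannot occur. A mean of 97.7% leaves a total shortfall of 20 × 2.3 = 46 points. Even if one woman carried all of it, the sample SD would be 46 / √20 = 10.3 points, far below 20.

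It is also fair to object to replacing the test by a pass rule on the observed mean. At a true 88%, a rule of observed mean at least 90% would be met in 20-36% of simulated trials, against 1-7% for the t-test. Such a rule is a debatable trade-off and is not proposed here.

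**Conclusion.** The point holds as a mismatch between the primary analysis, Aim 2 and the stated purpose of the trial. The equality of null and hypothesised value, and the conflict with 2.1, 9.1 and 9.2, are plain on the text and need no assumption.

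The size does need assumptions: 20 women, 20 sessions, one-sided 5% and SD 10 to 20 points. Under these the test succeeds in about 9-15% of trials at exactly 90% adherence and about 32-44% at 93%. The range depends strongly on the SD, which the documents do not give; near 5 points the shortfall in power above 90% largely goes away, though the null still equals the hypothesis. The excess over the nominal 5% is a separate fault, due to the ceiling at 100%.

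The consequence is a primary result that can mislead. Should-fix.

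**What to change.** Replace the adherence t-test sentence in 9.3.1 with:

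> The primary result is the mean percentage of the 20 prescribed sessions completed per woman randomised to exercise, with a 95% beta-binomial or bootstrap confidence interval, and the number of women at or above 90%. The estimate and interval are described against the 90% target, and no p-value is computed.

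Replace the retention t-test in the next sentence with the retained proportion and an exact binomial interval, since the same disclaimers apply and the outcome is binary. Changing only the adherence sentence would leave the conflict with 2.1, 9.1 and 9.2 in place.

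If the sponsor wants to keep an adherence test, its null should be a minimum acceptable adherence below 90%, fixed before data are seen, with a stated alpha and sidedness and a method suited to bounded data. Sections 2.1, 9.1 and 9.2 would then need to say that one test is planned.

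Section 9.3.1 should also say how unreturned logs are counted, because 8.1 has the logs handed in at the final visit.

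The cost is a short edit to one paragraph. The trial gives up the claim that adherence was shown to exceed 90%, and gains an estimate with stated precision, which is what 9.1 asks for.

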6.4.3 Recruitment and Retention Strategies

Participants will be recruited primarily through referrals at the research site. If necessary, participants may be recruited through community partnerships through fliers and word of mouth recruiting.

Because the intervention is only 10 weeks in duration with a five week follow up, we do not anticipate major issues with participant retention. We have experience conducting several previous PA trials in cancer survivors and typically observe only ~5% loss to follow-up in a short-term study. To encourage retention, participants will receive \$50 compensation at the baseline visit and again at the 10-week follow-up visit.

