7.7.2 Data Collection and Follow-up for Withdrawn Subjects

Data will be attempted to be gathered from participants who have withdrawn from the study to collect their data prior to their withdrawal, including emails from the research staff and telephone calls.

Withdrawn subjects will be analyzed using an intent to treat analysis, therefore maximizing the amount of data is paramount to success. However, if participants cannot be contacted after 3 attempts from the study team (both telephone calls and emails) then the participants will be considered lost to follow-up.

8 Study Procedures

Wait list interventions

After being randomized to the wait-list group, participants will be scheduled for their 10 week follow up visit. The wait list arm will not have the additional five week follow up that the exercise arm receives. Participants will be reminded that at that final visit, participants will complete the same study measures (body composition, functional fitness testing, blood sample collection, and anthropometrics) and will also receive study materials at the end of their wait list period. Participants in the wait list group will also complete accelerometer (Actigraph) assessments at three study points: Early in the intervention near the instructional visit, at the mid-way (5-week) mark, and before the final visit. These accelerometers will be sent and received via mail and participants will receive instructions on how to wear, use and send to us during the instructional visit.

Exercise interventions

After being randomized to the exercise (intervention) arm, participants will be scheduled for an instructional visit with the study coordinator within a week of randomization. At that visit, participants will be instructed to wear comfortable clothes and shoes for learning the exercises. The instructional visit includes going through each exercise of the intervention (see Table below) to learn the movement, learn the muscle groups involved, and to learn how to monitor themselves by tracking their progress via logs. This instructional visit should take 60-90 minutes, and each participant will receive a summary sheet of her starting point at each exercise with respect to intensity and progressions/regressions. For example, a participant may be starting on a blue resistance band for biceps curls, but the squats may simply be body weight at this time. Table below outlines the exercises for the intervention.

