8.5 Study Visits

8.4.1 Screening/Baseline:

Baseline. At this visit, the study coordinator will explain the study and obtain written informed consent. Physical measurements (anthropometrics, blood sample, DXA scan, functional fitness testing) will be completed. The study coordinator will instruct the participant on how to properly wear the accelerometer (to be returned via pre-paid mailer), complete a 7-day PA log, and complete the online questionnaires.

Randomization. After all baseline measures have been completed and checked, the participant will be randomized with 1:1 probability to the intervention or wait-list control group. A blocked randomization scheme will ensure equal allocation of participants to each group. Participants will be notified of their group assignment by phone; those in the intervention group

Table 4. Acceptable Window for Study Visits (including weekends)

Visit	Window	Activities
Randomization	+/- 5 days	Allocate to group
Instructional visit	+/- 2 weeks	Teach exercises, learn how to interface with software, how to log exercises
Final visit	+ /- 2 weeks	Collect final measures

8.4.3 Unscheduled:

- Pain or concerns that need to be addressed in person
- Adverse event follow ups with PCP

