12.32 Subject Stipends or Payments

Participants will be paid \$50 in cash at the baseline visit as well as another \$50 cash at the final (post-intervention) visit. Those who complete the intervention will receive a total of \$100 cash.

13 Publication Plan

The primary responsibility for publication of the results of this study are the investigators at UW Madison ([name]). Neither the complete nor any part of the results of the study carried out under this protocol, nor any of the information provided by the sponsor for the purposes of performing the study, will be published or passed on to any third party without the consent of the study sponsor. Any investigator involved with this study is obligated to provide the sponsor with complete test results and all data derived from the study.

14 Protocol implementation timeline and contingency plans

There are three primary concerns for this research design and there are listed preliminary contingency plans if these concerns come to fruition:

- The primary concern is a lack of subjects or low accrual to study participant goals for site numbers.
 - If there is insufficient or slow recruitment through a clinical route, we plan to reach out to community support groups such as Gilda's Club to bolster recruitment numbers. This strategy will not replace the clinical route, but may increase participant enrollment.
- The secondary concern is high attrition in the treatment group and potential losses to follow up over the course of the 10-week intervention. Although this is a lower probability event, we will utilize the following contingency plans:
 - Deploy follow ups using a support person for the participant that we can contact if the participant is not contacting study staff or seems to be lost to follow up
 - At the start of the study, we will collect multiple email addresses and phone numbers from

each participant to avoid this problem *a priori*.

- Finally, we may have poor adherence and compliance to the protocol.
 - We have pre-scheduled check-ins during the course of the intervention to avoid this issue
 - However, we will deploy additional health coaching if necessary where participants are really struggling with adherence
 - Participant satisfaction surveys will be used at the end of the intervention to evaluate the quality of the study to learn and improve for the future if adherence is very high

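### The planned one-sample t-test of retention against 90% treats a yes/no outcome as continuous: with all 40 women counted it has no value at 40/40 and gives p = 0.0023 at 39/40, where the exact p is 0.0805

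*Combined protocol and SAP*

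**What the plan says.** Section 9.3.1, under Primary Analysis, plans two one-sample t-tests against 90%. The first concerns the percentage of prescribed sessions completed, which is a genuine per-woman percentage and is not at issue here. The second reads: "A one-sample t-test will be done to determine if retention is >90" (per cent). It serves the Aim 1 hypothesis in section 2.2 that "we will meet the accrual goal and maintain >90% retention".

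The plan gives no formal definition of retention. Section 7.7.1 lists reasons for withdrawal. Section 7.7.2 says that women who cannot be reached after three attempts "then the participants will be considered lost to follow-up". Both describe a status that a woman either has or does not have.

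Section 9.3 defines three analysis populations but assigns none of them to retention. No alpha is stated. The direction is implied only by the wording that retention exceeds 90%. No exact test or confidence interval for the proportion is planned. Sections 2.1, 9.1 and 9.2 say that the trial is descriptive and is not meant for hypothesis testing.

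**The concern.** A one-sample t-test estimates its standard error from the spread of the observed values. For zeros and ones that spread is fixed by the observed proportion and vanishes as the proportion approaches 1. The plan expects to land in that region: section 6.4.3 says the investigators "typically observe only ~5% loss to follow-up in a short-term study". There the test either makes the evidence look much stronger than it is or yields no statistic at all.

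Retention is half of Aim 1's hypothesis, and the pilot exists to inform a larger study. An overstated claim that retention exceeds 90% could carry into that study's planning. A test also sits badly with a plan that says it is not testing hypotheses.

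**Working it through.** **Inputs.** Null value 90% (sections 2.2 and 9.3.1). Accrual goal 40 (sections 6 and 9.1). Allocation 1:1 in blocks, "A blocked randomization scheme will ensure equal allocation of participants to each group" (section 8.4.1), so about 20 per arm. Expected loss about 5% (section 6.4.3). The plan states no alpha, so one-sided 0.05 and 0.025 are used as assumptions. It reports no figure for this test that could be reproduced.

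**Formulas.** With k of n women retained and m = k/n:
- s = √[n·m(1−m)/(n−1)] and t = (m − 0.90)/(s/√n), on n−1 degrees of freedom, upper tail.
- Exact one-sided p = P(X ≥ k), where X is binomial(n, 0.90).

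**All 40 randomised women counted.**

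| Retained | s | t | t-test p (one-sided) | Exact p | Exact 95% CI |
|---|---|---|---|---|---|
| 38/40 | 0.2207 | 1.433 | 0.0800 | 0.2228 | 83.1–99.4% |
| 39/40 | 0.1581 | 3.000 | 0.0023 | 0.0805 | 86.8–99.9% |
| 40/40 | 0 | undefined | none | 0.0148 | 91.2–100% |

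At 39/40 the standard error is 0.1581/√40 = 0.025, so t = (0.975 − 0.90)/0.025 = 3.0. Other standard methods for a proportion lie near the exact result: score p = 0.057 and mid-p = 0.048. Two-sided, the contrast is 0.0047 against 0.18. The matching 95% t interval is 92.4% to 102.6%, which goes above 100%.

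At 40/40 at least one common package (scipy) returns an infinite t and p = 0.0 with a precision warning, so an undefined result can be printed as a success.

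**How likely are these results?** At true retention of 95%:
- P(39/40) = 40 × 0.95³⁹ × 0.05 = 0.271
- P(40/40) = 0.95⁴⁰ = 0.129

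**Type I error at true retention of 90%.** P(39/40) = 0.0657 and P(40/40) = 0.0148. The t-test rejects at 39/40 but not at 38/40. Its size is therefore 6.6% if 40/40 is left as no result, and 0.0657 + 0.0148 = 8.0% if it is counted as a success. These values are the same at nominal one-sided 0.05 and 0.025.

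**If accrual falls short.** With exactly one loss the standard error is 1/n, so t = (n−1) − 0.9n = 0.1n − 1. At one-sided 0.05 the t-test accepts one loss from n = 28 (p = 0.0415; 0.0505 at n = 27). The exact test does so only from n = 46 (p = 0.0480; 0.0524 at n = 45). At n = 28 the type I error is 28 × 0.9²⁷ × 0.1 = 16.3%, or 21.5% once 0.9²⁸ = 5.2% is added for no losses.

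**Exercise arm only, n = 20.** Two passages allow this reading. Aim 1 speaks of the "feasibility of recruiting and retaining endometrial cancer survivors to a home-based resistance training", and section 14 says "The secondary concern is high attrition in the treatment group".
- 19/20: t = 1.0, p = 0.165, exact p = 0.392. Neither test rejects.
- 20/20: undefined, exact p = 0.122. Its probability at true retention of 95% is 0.95²⁰ = 36%.
- Type I error: 0% if 20/20 is left as no result, 12.2% if it is counted as a success.

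**The case against.** The strongest reply is that little turns on this.

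- **Few results change.** With 40 women and a one-sided 0.05 level, only 39/40 changes the pass/fail result. At 38/40, the result that 5% loss implies, both tests fail. At 40/40 the exact test passes, as a careless reading of software output also would. This is correct.
- **The comparator is conservative.** At one-sided 0.05 the exact test passes only 40/40, so its true size is 1.5%, and the t-test's 6.6% to 8.0% is nearer to nominal. Mid-p passes 39/40 at 0.05. This weakens any claim that success at 39/40 is plainly false at that level. It does not rescue a p-value of 0.0023 when the score, mid-p and exact values are all 0.048 or more, nor the size at 0.025, nor an interval above 100%.
- **The 39/40 contrast depends on an unstated denominator.** True, and it disappears if only the exercise arm counts. The undefined statistic remains under either reading, and the missing denominator itself needs fixing.
- **The yes/no definition is inferred.** Also true. But withdrawal, loss to follow-up and visit completion are each yes/no for a given woman.
- **The stakes are low.** Retention is not a listed endpoint in sections 4.1.1 or 4.1.2, the trial describes itself as descriptive, and readers will see the raw count. This limits the severity. It does not make the named test suitable.

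**Conclusion.** The concern holds. Applied as written, the test gives a misleading p-value or none for results the plan has good reason to expect. If all 40 women are counted and true retention is 95%, these two results have probabilities of 27% (39/40) and 13% (40/40). The type I error is 6.6% to 8.0% at full accrual, and higher if accrual ends between 28 and 39.

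The figures for 39/40 assume that all randomised women form the denominator, and the pass/fail statements assume a one-sided level of 0.05 or 0.025. The undefined statistic at full retention depends on neither assumption. This should be corrected before analysis. It does not threaten the trial, because no go/no-go decision rests on the p-value.

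**What to change.** Replace the retention sentence in section 9.3.1 with wording such as:

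> Retention is the number of randomised women who complete the 10-week final visit divided by all women randomised. It will be reported overall and by arm with an exact (Clopper–Pearson) 95% confidence interval.

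This settles the definition and the denominator together. The 10-week visit is the last that both arms share, since "The wait list arm will not have the additional five week follow up that the exercise arm receives" (section 8).

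Aim 1's own criterion can be kept by comparing the observed proportion with 90%. With 40 women that means at least 37 retained (36/40 is exactly 90%). Its properties should be stated: it is met with probability 86%, 42% and 13% at true retention of 95%, 90% and 85%.

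If a test is kept, it should be exact binomial with alpha and sidedness stated, noting that at one-sided 0.05 only 40/40 passes. The adherence t-test needs no change on this account.

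The cost is one or two sentences and no new data. There are three drawbacks. No p-value will support the retention claim. The point-estimate comparison is lenient near 90%. The by-arm intervals are wide (75.1–99.9% at 19/20, 83.2–100% at 20/20).

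### The plan rules out hypothesis testing at this size, yet sets within- and between-group ANOVAs on about 15 to 17 outcomes with no alpha, key outcome or limit on interpretation

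*Combined protocol and SAP*

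**What the plan says.** Three sections disclaim testing. Section 2.1, in the overview of the proposed research, says that in small samples "the true effect size is more likely to be under or overestimated, therefore hypothesis testing is not valid". Section 9.1 says "The purpose of this trial is not to conduct hypothesis testing, but rather to field-test the intervention" and adds that "the anticipated effect size is unknown" and that "the sample size of 40 has been selected to maximize feasibility in the anticipated time frame for this project". Section 9.2 says "we have a feasibility/descriptive focus as opposed to a hypothesis-testing focus".

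Section 9.3.1 then sets the secondary analyses, covering pre-to-post changes and differences between groups: "Paired ANOVAs and descriptive statistics will be used to analyze functional and objective data". The same sentence extends to participant feedback data. The statistical methodology row of the synopsis lists paired comparisons within groups and comparisons between groups. The exploratory bullet of 9.3.1 adds longitudinal analyses "to estimate potential magnitude of expected changes". The primary analysis in 9.3.1 consists of two one-sample t-tests against 90%, one for adherence and one for retention.

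No section gives an alpha, a multiplicity rule, a key secondary outcome or a rule for reading a secondary p-value.

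**The concern.** ANOVA is a significance test. A plan that calls testing invalid at its own sample size and then names a test as the method for its secondary outcomes leaves the analyst with two incompatible instructions. Nothing in 9.3.1 says which one governs the report.

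With many outcomes and no rule for interpreting the results, some p-values below 0.05 can be expected even if training changes nothing, and a reader may take them as effects of training. The outcomes that reach significance will also tend to show exaggerated differences. That is the misestimation section 2.1 warns of, and the planned magnitude estimate has no stated interval to show how uncertain it is.

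**Working it through.** The plan has no figure to reproduce: 40 is a feasibility number, with no alpha, power, effect size or SD behind it. The steps below size the problem.

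**Inputs from the documents**
- Sample: 40, and "the participant will be randomized with 1:1 probability to the intervention or wait-list control group" (Screening/Baseline, under 8.5), so about 20 per arm. Section 6.4.3 expects about 5% loss, so about 19 per arm at week 10.
- Outcomes in 8.1: six functional tests, two biomarkers (A1c, CRP), three anthropometric measures that can change (weight, waist, hip) and four DXA measures. 6 + 2 + 3 + 4 = 15.
- Adding accelerometer MVPA and steps, which 8.1 gives only as examples: 15 + 2 = 17.
- Adding the questionnaires: FACT-En as one score (two if the general score and the endometrial subscale are separate), three PROMIS domains and one self-efficacy scale. 17 + 5 = 22, or 17 + 6 = 23.
- Contrasts per outcome: pre-post in each arm (two) and between arms (one). The synopsis could be read as asking for between-group comparisons at two times, which would add more.

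**Assumptions, not in the documents:** 5% two-sided per test; no mean change in either arm; equal correlation between outcomes of 0 to 0.7.

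**Between-arm tests only, 17 outcomes**
- Expected false positives: 17 × 0.05 = 0.85. Correlation does not alter this.
- Chance of at least one if independent: 1 − 0.95^17 = 0.58.
- With correlated outcomes (simulated two-sample t-tests, 20 per arm): about 0.50 at correlation 0.3, 0.39 at 0.5 and 0.28 at 0.7.

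**Adding the two within-arm tests per outcome**
- 17 × 3 = 51 tests; 51 × 0.05 = 2.55, about 2.6 expected.
- The three tests on an outcome are not independent, because the between-arm contrast is the difference of the two within-arm changes. Simulating all three from the same data gives a chance of at least one of about 0.88 with uncorrelated outcomes and about 0.53 at correlation 0.7 (simulation error under one percentage point).

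**With the questionnaires, 22 outcomes**
- Between-arm only: 22 × 0.05 = 1.1 expected; 1 − 0.95^22 = 0.68 if independent.
- All three contrasts: 66 × 0.05 = 3.3 expected. The chance of at least one is about 0.93 with uncorrelated outcomes, 0.75 at correlation 0.5 and 0.57 at 0.7.

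**Precision of one between-arm difference** (in SDs of the change)
- 20 per arm: t(0.975, 38) × √(2/20) = 2.024 × 0.316 = 0.64.
- 19 per arm: t(0.975, 36) × √(2/19) = 2.028 × 0.324 = 0.66.
- So an observed difference must reach about 0.64 SD to be significant. With 20 per arm, power is 15% for a true difference of 0.3 SD and 34% for 0.5 SD, and 80% power needs 0.91 SD. When the true difference is 0.3 SD, the results that reach significance show an average absolute difference of about 0.82 SD.

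**The case against.** The best defence is that the plan is openly a pilot with adherence as its primary endpoint. It pairs the ANOVAs with descriptive statistics, states a descriptive focus in 9.2, and says in the exploratory bullet that formal testing lies outside its aims. That describes the plan's intent fairly, but the last caveat sits only in the exploratory bullet. It does not reach the secondary bullet, which names the ANOVAs.

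The defence does succeed against several stronger readings that a reader might infer:

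- *ANOVAs on more than 20 outcomes.* The sentence names functional and objective data, which come to 15 to 17. The questionnaires are repeated at mid-point and fit the exploratory longitudinal analyses. Aim 3 does group patient-reported outcomes with functional and objective assessments, so 22 to 23 is a possible reading, but not a stated one.
- *A near-certain false positive.* Treating 66 tests as independent gives 1 − 0.95^66 = 0.97. That independence cannot hold here, for the reason shown in the working.
- *Chance findings will be reported as training effects.* No section sets such a reporting rule. The documents support only that nothing prevents it.
- *The observed effect will size the larger trial.* No section says so. Section 2.1 speaks of carrying logistical components forward.
- *Estimating a magnitude is itself a contradiction.* Estimation is not testing. The weakness is the lack of a required interval or caution.

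**Conclusion.** Wrong as written. The disclaimers in 2.1, 9.1 and 9.2 and the analyses in 9.3.1 and the synopsis cannot all stand, and no other section resolves the conflict.

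On the narrower count of outcomes, the exposure is a material risk and not a certainty: roughly one between-arm false positive expected, or two to three if within-arm tests are also run. These figures rest on the assumed 5% level, the assumed range of correlation and my count of outcomes from 8.1. The contradiction itself rests on none of them.

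The primary analysis has the same conflict, since its two one-sample t-tests are also hypothesis tests. The multiplicity figures concern the secondary outcomes only.

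**What to change.** In 9.3.1 and the statistical methodology row of the synopsis:

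1. Replace the ANOVA tests with the estimated between-arm difference in change and its 95% confidence interval for each quantitative secondary outcome measured in both arms. Label these descriptive, and give no p-values or significance claims.
2. Summarise satisfaction and interview data descriptively. The exit interviews are held in the intervention arm, so a between-arm difference does not apply to them.
3. State that any magnitude of expected change is reported with its interval and will not be used alone to size the larger study. Carrying forward the SD of change with an upper confidence limit is one optional planning convention; nothing in the documents requires it.
4. Reconcile the adherence and retention t-tests with 2.1, either by reporting each as an estimate with an interval beside the 90% target or by stating why these two tests are exempt.

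The cost is wording only; no visit, measure or procedure changes. The downside is that no significance claim can be made on secondary outcomes, which section 2.1 already accepts.
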